## **3 STATISTICAL METHODS**

### **3.1 General Methods**

#### **3.1.1 Computing Environment**

All statistical analyses will be performed using SAS® Version 9.4 or higher for Windows.

#### **3.1.2 Reporting of Numerical Values**

All clinical study data will be presented in subject data listings. All by-visit summarizations will be conducted using data from Cycle 1, Cycle 2, and/or the last cycle, as applicable. All data presentations will be by the planned cohorts in the protocol, separately for Phase 1 and Phase 2.

Descriptive statistics (n, mean, standard deviation, median, minimum and maximum) will be calculated by cohort for continuous variables.

Frequencies and percentages will be presented by cohort for categorical and ordinal variables. If there are missing values, the number missing will be presented, but without a percentage.

Means and medians will be reported to one decimal place more than the data reported in the EDC. Standard deviations will be reported to two decimal places more than the data reported. Minimum and maximum will be reported to the same number of decimal places captured in the EDC.

#### **3.1.3 Baseline Value and Change from Baseline**

Baseline value is defined as the most recent non-missing value obtained immediately prior to administration of first dose. Change from baseline will be calculated by subtracting the baseline value from the post-treatment assessment for each subject (i.e., post-treatment – baseline).

#### **3.1.4 Handling of Missing/Incomplete Values**

Unless otherwise explicitly specified, missing data will not be imputed.

#### **3.1.5 Handing of Repeated Assessments**

If multiple results are available for a test at the same scheduled time point post-baseline then the following rules will be used:

- If multiple pre-dose assessments are available at the same scheduled time point and all results are considered normal, then the first (earliest) result will be used in all summarizations.
- If multiple pre-dose assessments are available at the same scheduled time point and at least one result is considered abnormal, then the worst (most abnormal) result will be used in the summarization.

## **3.2 Analysis Populations**

### **3.2.1 Intent-To-Treat Population**

The Intent-To-Treat (ITT) Population and the Safety Population are the same for this study and are defined as all subjects who receive at least one dose of PLD, motolimod (pre Amendment 2), or MEDI4736. All tables, listings, and figures will identify this group of subjects as the Intent-to-Treat Population.

### **3.2.2 Per-Protocol Population**

The Per-Protocol (PP) Population is defined as all subjects enrolled in Phase 2 of the study, including the 6 subjects treated in Phase 1 at the MTD, who received at least 75% of the scheduled doses of MEDI4736 and PLD over the first 2 cycles, as well as respective disease assessments, without major protocol violations.

**Phase 2:** The Per-Protocol (PP) Population for Phase 2 is defined as all subjects enrolled in Phase 2 of the study who received at least 75% of the scheduled doses of MEDI4736 and PLD over the first 2 cycles, as well as respective disease assessments, without major protocol violations.

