### **3.8 Efficacy Analysis**

#### **3.8.1 Progression-free Survival**

The primary endpoint in Phase 2 of this study is the PFS rate at 6 months defined as the visit at the start of Cycle 7, where progression is assessed for subjects based on a combination of RECIST v1.1 and/or the clinician's assessment of clinical progression or death. The primary efficacy analysis will be based on the Per Protocol population. A sensitivity analysis will be conducted on the ITT population. A secondary efficacy analysis will be conducted on the Phase 2 Per Protocol population.

The primary efficacy analysis entails testing the null hypothesis that PFS at 6 months is less than or equal to 25% against the alternative hypothesis that PFS at 6 months is higher for those treated with PLD and MEDI4736 combination. This hypothesis will be tested at  $\alpha=0.05$  using the 90% two-sided confidence interval for the PFS rate at 6 months based on Kaplan-Meier product limit estimates. The null hypothesis will be rejected in favor of the alternative if the lower bound of that confidence interval is greater than 25%. The null hypothesis will also be tested using a one-sided binomial test as a sensitivity analysis. In this analysis, if a subject has no tumor response assessment, or discontinued treatment or withdrew from the study for other reasons, he or she will be considered as "progressed." The null hypothesis will be rejected in favor of the alternative if the lower bound of a two-sided 90% binominal confidence interval is greater than 25%.

Table displays will include PFS rate at 6 months and the corresponding 90% confidence interval along with the corresponding number of subjects at risk. In addition, PFS will be presented graphically.

Secondary efficacy analyses will use the secondary efficacy endpoints listed in section 3.3.1 of the SAP and will be based on the ITT population. PFS rate and the corresponding 95% confidence interval will be calculated based on Kaplan-Meier product limit estimates and will be displayed by cohort and phase.

Descriptive analyses of PFS will include the following:

- Number and percentage of subjects that died or had a confirmed progression,
- Number and percentage of subjects that survived without a confirmed progression,
- Number and percentage of subjects lost to follow up (unknown survival and/or progression status), and
- Number of subjects missing the tumor response assessment

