## 4 LIST OF TABLES

Table 14.1.1	Subject Disposition, All Subjects
Table 14.1.2	Demographics and Baseline Characteristics, ITT Population
Table 14.1.3	Demographics and Baseline Characteristics, Per-Protocol Population
Table 14.1.4	Non-Oncological Medical History, ITT Population
Table 14.1.5	Concomitant Medication, ITT Population
Table 14.1.6	Treatment Exposure, ITT Population
Table 14.2.1.1	Progression-free Survival (PFS) Based on RECIST v1.1, Per-Protocol Population
Table 14.2.1.2	Progression-free Survival (PFS) Based on RECIST v1.1, ITT Population
Table 14.2.2.1	Summary of Progression-free Survival (PFS) Based on RECIST v1.1, ITT Population
Table 14.2.2.2	Summary of Progression-free Survival (PFS) Based on irRECIST, ITT Population
Table 14.2.3.1	Summary of Tumor Response, Overall Response Rate and Overall Disease Control Rate Based on RECIST v1.1 Criteria, ITT Population
Table 14.2.3.2	Summary of Tumor Response, Overall Response Rate and Overall Disease Control Rate Based on irRECIST Criteria, ITT Population
Table 14.2.4	Summary of Overall Survival (OS), ITT Population
Table 14.3.1	Summary of Adverse Events, ITT Population
Table 14.3.2	Incidence of Treatment Emergent Adverse Events by MedDRA System Organ Class and Preferred Term, ITT Population
Table 14.3.3	Incidence of Treatment Emergent Adverse Events by MedDRA Preferred Term, ITT Population
Table 14.3.4	Incidence of Treatment Emergent Adverse Events by Maximum CTCAE Grade, MedDRA System Organ Class and Preferred Term, ITT Population
Table 14.3.5.1	Incidence of Treatment Related Adverse Events by MedDRA System Organ Class and Preferred Term, ITT Population
Table 14.3.5.2	Incidence of MEDI4736 Related Adverse Events by MedDRA System Organ

Class and Preferred Term, ITT Population

Table 14.3.5.3	Incidence of Motolimod Related Adverse Events by MedDRA System Organ Class and Preferred Term, ITT Population
Table 14.3.5.4	Incidence of Pegylated Liposomal Doxorubicin (PLD) Related Adverse Events by MedDRA System Organ Class and Preferred Term, ITT Population
Table 14.3.6.1	Incidence of Treatment Related Adverse Events By Maximum CTCAE Grade, MedDRA System Organ Class and Preferred Term, ITT Population
Table 14.3.6.2	Incidence of MEDI4736 Related Adverse Events By Maximum CTCAE Grade, MedDRA System Organ Class and Preferred Term, ITT Population
Table 14.3.6.3	Incidence of Motolimod Related Adverse Events By Maximum CTCAE Grade, MedDRA System Organ Class and Preferred Term, ITT Population

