## 6 LIST OF FIGURES

Figure 1.1.1	KM Estimate of Progression-free Survival based on RECIST v1.1, Phase 1 Cohort Dose Level +1 and Phase 2 Combined Per-Protocol Population
Figure 1.1.2	KM Estimate of Progression-free Survival based on RECIST v1.1, Phase 2 Per-Protocol Population
Figure 1.2	KM Estimate of Progression-free Survival based on RECIST v1.1, Phase 1 Cohort Dose Level +1 and Phase 2 Combined Intent-to-Treat Population
Figure 2.1	KM Estimate of Progression-free Survival based on RECIST v1.1 by Cohort, Intent-to-Treat Population
Figure 2.2	KM Estimate of Progression-free Survival based on irRECIST by Cohort, Intent-to-Treat Population
Figure 3	KM Estimate of Overall Survival by Cohort, Intent-to-Treat Population

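### Does pooling six motolimod-exposed Phase 1 subjects undermine a primary hypothesis worded for PLD plus MEDI4736?

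*SAP*

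**What the plan says.** The alternative hypothesis in SAP 3.8.1 is that "PFS at 6 months is higher for those treated with PLD and MEDI4736 combination", tested against a null of 25% or less. The primary analysis uses the Per-Protocol population, which SAP 3.2.2 defines as "all subjects enrolled in Phase 2 of the study, including the 6 subjects treated in Phase 1 at the MTD", subject to the dosing, assessment and protocol-violation criteria. SAP 2.2 says that all subjects received motolimod before Amendment 2, at 2.5 mg/m² for level +1.

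SAP 3.2.2 also defines a Per-Protocol set for Phase 2 subjects alone, and 3.8.1 adds: "A secondary efficacy analysis will be conducted on the Phase 2 Per Protocol population". The figure list (SAP 6) keeps the two sets apart. Figure 1.1.1 is for the "Phase 1 Cohort Dose Level +1 and Phase 2 Combined Per-Protocol Population", and Figure 1.1.2 is the "KM Estimate of Progression-free Survival based on RECIST v1.1, Phase 2 Per-Protocol Population".

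On interval levels, 3.8.1 sets a two-sided 90% interval for the primary test, then says that the tables will show the 6-month PFS rate with its 90% interval. A later paragraph reads: "Secondary efficacy analyses will use the secondary efficacy endpoints listed in section 3.3.1 of the SAP and will be based on the ITT population". It continues: "PFS rate and the corresponding 95% confidence interval will be calculated based on Kaplan-Meier product limit estimates".

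In the protocol, the Synopsis and 3.1.5 plan for the six MTD subjects to count towards the 41. Section 3.1.6 sets the 45% target for motolimod plus MEDI4736 with standard of care, and notes that motolimod was then discontinued under Amendment 2.

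**The concern.** Once motolimod was dropped, the SAP hypothesis named two drugs, but the set used to test it still holds six subjects who had three. The protocol's 45% target was written for three drugs. Read strictly, neither text describes the mixture analysed, and a positive result could be credited to PLD plus MEDI4736 when part of it came from motolimod-exposed subjects.

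Three further points seem to leave the Phase 2-only analysis too loose to settle the matter:

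- It is called secondary, and nothing says that it carries a conclusion about the two drugs.
- Both 90% and 95% appear in 3.8.1 and neither is tied to it by name. The only Per-Protocol PFS table title is "Progression-free Survival (PFS) Based on RECIST v1.1, Per-Protocol Population".
- SAP 2.2 reports one patient already enrolled in Phase 2 when motolimod stopped, so even that set may not be free of motolimod.

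At stake would be the error rate and power of the primary test, and a choice between two verdicts after the data are seen.

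**Working it through.** **Inputs.** Null 0.25, alternative 0.45, one-sided alpha 0.05, exact single-proportion test, 41 evaluable subjects and 80% power (protocol 3.1.6). Six of the 41 come from Phase 1 (protocol 3.1.5, SAP 2.2.1), which leaves 35. Rates among the six are assumptions, because the documents give none.

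**1. The plan's own figure.** The cut-off is the smallest r with P(X ≥ r | n, 0.25) ≤ 0.05. For n = 41, P(X ≥ 15) = 0.0666 and P(X ≥ 16) = 0.0333, so r = 16. Power is P(X ≥ 16 | 41, 0.45) = 0.8225. The stated 80% holds.

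**2. Pooled test when the six differ.** Let pd be the rate in the 35 and pm the rate in the six.

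P(reject) = Σ (k = 0 to 6) Bin(k; 6, pm) × P(Bin(35, pd) ≥ 16 − k)

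| pm | pd = 0.25 (error) | pd = 0.45 (power) |
|---|---|---|
| 0.25 | 0.0333 | 0.7100 |
| 0.35 | 0.0532 | 0.7699 |
| 0.40 | 0.0655 | 0.7971 |
| 0.45 | 0.0796 | 0.8225 |
| 0.50 | 0.0955 | 0.8461 |

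Error crosses 0.05 at pm ≈ 0.336, and power crosses 0.80 at pm ≈ 0.406. A 10-point advantage for motolimod under the null (pm = 0.35) gives 5.3% error. With the other 35 at 45%, power stays at 80% or more for any pm above about 0.41, so the 80% does not require motolimod to have no effect at all.

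**3. Phase 2-only analysis, n = 41 − 6 = 35.**

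| Interval | Cut-off | Error | Power |
|---|---|---|---|
| 90% two-sided | 14/35 | 0.0363 | 0.7767 |
| 95% two-sided | 15/35 | 0.0158 | 0.6624 |

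**4. Which level applies?** The first paragraph of 3.8.1 lists three analyses of the primary endpoint: Per-Protocol, ITT and Phase 2 Per-Protocol. The 90% rule and the 90% table display follow directly. The 95% sentence comes later, in a paragraph confined to secondary endpoints in the ITT population. A Per-Protocol analysis of the primary endpoint meets neither condition, so 90% is the natural reading.

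**5. Can the two verdicts differ?** With k of the six progression-free, the pooled rule needs 16 − k of the 35, and the Phase 2-only rule needs 14. They coincide for every Phase 2 count only at k = 2. At k = 3, 13/35 passes pooled and fails alone (p = 0.0756). At k = 1, 14/35 passes alone and fails pooled. With equal true rates the verdicts differ with probability 0.0096 + 0.0127 = 0.0223 at 25%, and 0.0681 + 0.0223 = 0.0904 at 45%.

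**6. Kaplan-Meier form.** With no censoring before Cycle 7, the Kaplan-Meier estimate is the simple proportion. Untransformed and log-log 90% intervals then give the same cut-offs, 16/41 and 14/35. A log-transformed interval gives 15/41 and 13/35. With earlier censoring these figures are indicative only.

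**The case for a change.** The strongest case for a change is that the decision should be fixed before results are known and that fixing it costs only a few sentences. The hypothesis could read PLD plus MEDI4736 with or without prior motolimod. The Phase 2-only analysis could be given its level and a table title and named as the basis for any two-drug statement, after dosing records are checked for the one early Phase 2 subject. The verdicts can split, and a reader who takes the word secondary to imply 95% moves the cut-off from 14 to 15 of 35.

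The mismatch in wording stands, and so does the fact that no level is explicitly attached to the Phase 2-only analysis. The rest does not amount to a defect:

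- The pass/fail rule is not open. Pooled Per-Protocol is primary and Phase 2 Per-Protocol is secondary. Split verdicts of 2.2% and 9.0% are computed with no motolimod effect; they come from comparing overlapping sets of different size.
- All six were assigned PLD and MEDI4736 at the Phase 2 dose level, so the wording is incomplete for them rather than false. Motolimod doses are summarised under SAP 3.7 and drug administration is listed.
- The table list gives titles only. SAP 3.1.2 calls for separate presentation by phase and 3.2.2 uses the Per-Protocol name for both sets, so Table 14.2.1.1 can hold both.
- SAP 2.2 says that one patient was enrolled when motolimod stopped, not that she was dosed. If she was, and she were removed, the cut-off stays at 14 (of 34) with 73.1% power.

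**Conclusion.** No change is needed. The mismatch is real but small: six of 41 subjects, pooled as the protocol planned, labelled as such, with the Phase 2-only result reported alongside. The suggested additions would put into words what the planned analyses already show. They would alter no decision rule and correct no demonstrated bias. An analyst following the SAP as written would report the pooled primary result and the Phase 2-only estimate with a 90% interval, and could describe the motolimod exposure of the six from the dosing data.

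The size of any distortion cannot be known from the documents. Pooled error exceeds 5% only if the six do roughly 9 points better than a 25% rate in the rest. Power falls below 80% only if they do more than about 4 points worse than a 45% rate in the rest. Protocol section 2 reports no significant PFS or overall survival gain from motolimod added to PLD. That gives no support for a large effect, although that study did not include MEDI4736. The conclusion assumes 35 Phase 2 subjects, the exact rule (or an untransformed or log-log interval with no censoring before Cycle 7), and the 90% reading of 3.8.1.

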4.1.1.1 Progression-free Survival Rate

The proportion of subjects who survive and do not progress - Progression Free Survival (PFS) rate- within the first 6 months of treatment based on RECIST v1.1 evaluated for the per-protocol analysis population constitutes the primary endpoint in Phase 2 of the study. PFS rate at 6 months will be based on disease assessments at the scheduled visit at the start of Cycle 7.

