4.1.2 Subject Evaluation & Statistics

The Per-Protocol (PP) Population for clinical efficacy is defined as all subjects who received at least 75% of the scheduled doses of MEDI4736, motolimod (pre Amendment 2), and PLD over the first 2 cycles, as well as respective disease assessments, without major protocol violations. The Intent-To-Treat (ITT) Population for clinical efficacy is defined as all subjects who receive at least one dose of PLD, motolimod (pre Amendment 2) or MEDI4736.

The analysis of clinical efficacy will be based on both the intent-to-treat (ITT) and the per-protocol (PP) populations.

The PFS Rate at 6 months based on RECIST v1.1 evaluated for the per-protocol analysis population constitutes the primary endpoint in Phase 2 of the study. This PFS rate along with its one sided 95% Confidence Interval (CI) based on binomial distribution will be estimated and reported. The one-sided null hypothesis of 6-month PFS ≤ 0.25 will be rejected at 0.05 level of significance if the 95% one-sided CI does not contain 0.25. The 12-months PFS rate along with its 95% one-sided CI will be calculated and reported as a secondary endpoint.

Tumor Response will be summarized and analyzed descriptively for each cohort and analysis population. A 95% Confidence Interval based on binomial distribution will be constructed for the estimated ORR.

Median OS will be calculated using the Kaplan-Meier method. The analysis of PFS and OS will be updated based on data collected during the Post Study Follow-up (see Section 3.1.16).

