#### **2.2.3.2 Progression-free Survival Time**

Median PFS time evaluated using RECIST v1.1 and irRECIST criteria is a Phase 1 and Phase 2 secondary endpoint.

PFS time will be defined as the number of days from the date of first dose to the date of earliest disease progression based on radiological or clinical assessment or to the date of death, if disease progression does not occur. Every effort will be made to follow subjects for PFS if they complete or discontinue the study prior to progression.

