## **3.3 Analysis Variables**

### **3.3.1 Clinical Efficacy**

Tumor response will be assessed using RECIST v1.1 and irRECIST criteria. When a radiological assessment is unavailable to determine RECIST (irRECIST), a clinical assessment of progressive disease and/or death may be used in lieu of the RECIST (irRECIST) to determine disease response. This combined clinical efficacy endpoint will be used in the primary efficacy analysis. RECIST and irRECIST criteria are described in detail in the protocol, and an abbreviated description is provided below.

RECIST evaluation of target lesions are as follows:

Response	Criteria for Response
Complete Response (CR)	Disappearance of all target lesions
Partial Response (PR)	At least a 30% decrease in the sum of the diameters of target lesions taking as reference the baseline sum diameters
Stable Disease (SD)	Neither sufficient shrinkage to qualify for PR nor sufficient increase to qualify for PD
Progressive Disease (PD)	At least 20% increase in the sum of the diameters of target lesions taking as reference the baseline sum diameters or new lesion identification

irRECIST evaluation of target and new lesions are as follows:

Complete Response (irCR)	Complete disappearance of all target and new, measurable lesions, with the exceptions of lymph nodes which must decrease to < 10 mm in short axis.
Partial Response (irPR)	Decrease in TMTB* $\geq$ 30% relative to baseline.
Stable Disease (irSD)	Not meeting criteria for irCR or irPR, in absence of irPD.
Progressive Disease (irPD)	Increase in TMTB $\geq$ 20% relative to nadir.

\*TMTB = SumD target lesions + SumD new, measurable lesions.

For both RECIST and irRECIST, if CA125 levels are initially above the upper normal limit, they must normalize for a subject to be considered in complete clinical response.

Efficacy variables include:

- Progression-free Survival
  - Proportion of subjects surviving without progression at 6 months (based on RECIST v1.1 and/or clinical progression/death) – Phase 2 primary endpoint
  - Proportion of subjects surviving without progression at 6 months (based on irRECIST and/or clinical progression/death) – Phase 2 secondary endpoint
  - Proportion of subjects surviving without progression at 12 months (based on RECIST v1.1 and irRECIST and/or clinical progression/death) – Phase 2 secondary endpoints

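### The deciding 6-month PFS test drops, and lets the study replace, subjects who die or stop for clinical progression before the Cycle 2 doses, although the SAP counts those events as failures

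*SAP*

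**What the plan says.** The protocol and the SAP agree on the primary set. Protocol 4.1.1.1 states that the 6-month PFS rate "evaluated for the per-protocol analysis population constitutes the primary endpoint in Phase 2 of the study", and SAP 3.8.1 says: "The primary efficacy analysis will be based on the Per Protocol population. A sensitivity analysis will be conducted on the ITT population".

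Membership depends on exposure after treatment starts. SAP 3.2.2 admits subjects "who received at least 75% of the scheduled doses of MEDI4736 and PLD over the first 2 cycles, as well as respective disease assessments" and leaves out anyone with a major violation. Protocol 4.1.2 has the same rule: "all subjects who received at least 75% of the scheduled doses of MEDI4736, motolimod (pre Amendment 2), and PLD over the first 2 cycles". Neither makes an exception for a subject who missed doses because of death or progression. Protocol 3.1.11 allows Phase 2 subjects who are not evaluable per protocol to be replaced.

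The endpoint treats those events as failures. SAP 2.2.3.2 runs PFS time "to the date of earliest disease progression based on radiological or clinical assessment or to the date of death". SAP 3.3.1 adds that, when a scan is unavailable, "a clinical assessment of progressive disease and/or death may be used in lieu of the RECIST (irRECIST) to determine disease response", and says that this combined endpoint is used in the primary efficacy analysis.

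The null of 25% or less is tested "using the 90% two-sided confidence interval for the PFS rate at 6 months based on Kaplan-Meier product limit estimates" (SAP 3.8.1) and is rejected if the lower bound exceeds 25%. A binomial sensitivity analysis counts a subject as progressed if she "has no tumor response assessment, or discontinued treatment or withdrew from the study for other reasons".

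**The concern.** The population rule removes some of the events that the endpoint is built to count. A subject who fails in the first four weeks is a PFS failure by definition, but she cannot meet the dose rule, so she leaves both numerator and denominator and another subject may take her place. Removing known failures can only raise the observed rate relative to all treated subjects, and this is the rate that decides whether 25% is rejected.

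The protocol avoids the problem elsewhere. Its Per-Protocol set for DLT assessment (Protocol 4.2.2) keeps every subject with a DLT in the evaluation period and applies the 75% rule only to those without one. The efficacy set has no such safeguard.

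A second gap could widen the exclusion. No scan is scheduled in the first two cycles; the first on-treatment scan is at Cycle 4 Day 1, Day 85. If the disease-assessment condition means that scan, failures up to Day 85 could also be dropped. The text does not settle this.

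Early toxicity stops are a separate matter. They are not PFS events, and dropping them biases the rate only if those subjects fare worse than the rest.

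**Working it through.** **Who is excluded.** The Phase 2 schedule (SAP 2.2; Protocol 3.2 flowchart for all subjects except dose level 0a) gives PLD on Days 1 and 29 and MEDI4736 on Days 3 and 31. Before Day 29 a subject has at most 2/4 = 50% of doses.
- Pooled count: 75% of 4 is 3 doses, reached on Day 29.
- Per-drug count: 75% of 2 is 1.5, so both doses of each drug are needed, reached on Day 31.

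She is out on either count. The text does not say which applies; it matters only for a subject who has the Day 29 dose but not the Day 31 dose.

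**The plan's own figure.** Protocol 3.1.6 gives n = 41, null 0.25, alternative 0.45, one-sided alpha 0.05, exact test, 80% power. Exact binomial at n = 41:
- P(X ≥ 15 | 0.25) = 0.0666, too large
- P(X ≥ 16 | 0.25) = 0.0333, so reject at 16 or more
- P(X ≥ 16 | 0.45) = 0.8225

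The stated 80% holds, read as at least 80%.

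**The SAP's Kaplan-Meier rule.** With no censoring before 6 months the estimate is x/n and the Greenwood standard error is √(p(1−p)/n). The SAP does not state the interval type, so two are shown. Lower 90% two-sided bounds (plain / log-log) are 0.242 / 0.245 at 15 of 41 and 0.265 / 0.266 at 16 of 41. The cut-off is again 16.

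**Effect on type I error.** Let f be the share of treated subjects excluded and replaced, and q the share of the excluded who would have been progression-free at 6 months. With an all-treated rate of 0.25,

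PP rate = (0.25 − f·q)/(1 − f).

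Example: f = 10%, q = 0 gives 0.25/0.90 = 0.2778, and P(X ≥ 16 | n = 41, 0.2778) = 0.079.

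| f | PP rate, q = 0 | Type I error, q = 0 | PP rate, q = 0.10 | Type I error, q = 0.10 |
|---|---|---|---|---|
| 5% | 0.263 | 0.051 | 0.258 | 0.043 |
| 10% | 0.278 | 0.079 | 0.267 | 0.057 |
| 15% | 0.294 | 0.121 | 0.276 | 0.076 |
| 20% | 0.313 | 0.182 | 0.288 | 0.102 |

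The q = 0 columns are an upper bound, since every excluded subject fails. At q = 0.25 there is no bias and the error stays at 0.033. Replacement is not needed for the effect: with 41 treated and q = 0 exclusions not replaced, the error is 0.053, 0.081, 0.118 and 0.163 for the same f. Neither f nor q is given in the documents.

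**How many subjects change the decision.** Start from 16 of 41 and add back dropped early failures:

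| Result | Exact lower bound | KM plain | KM log-log |
|---|---|---|---|
| 16/41 | 26.2% | 26.5% | 26.6% |
| 16/43 | 24.9% | 25.1% | 25.3% |
| 16/44 | 24.3% | 24.4% | 24.7% |

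Two added failures reverse rejection under the exact rule, and three under all three intervals.

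**The case against.** The strongest reply is that Per-Protocol is the declared primary set in both documents and the sample size is stated in evaluable subjects. For that set the test keeps its level of 0.033; the error is inflated only if 25% describes all treated subjects. Protocol 3.1.6 ties the 25% to the population to be enrolled, which favours the all-treated reading, but the analysis sets behind the cited rate cannot be seen. This uncertainty stands.

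The plan also includes an ITT sensitivity analysis (Table 14.2.1.2, directly after the Per-Protocol table) and a binomial analysis counting dropouts as progressed. The ITT result would expose the bias. Neither governs rejection, however, and the binomial analysis names no population; run on the Per-Protocol set, it cannot recover excluded subjects.

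The group may be small. Eligibility requires ECOG 0 or 1 and excludes platinum-refractory disease and gastrointestinal obstruction, and no scheduled scan can trigger exclusion this early. Keeping 41 after excluding 15% or 20% means about 7 or 10 exclusions (41/0.85 − 41 = 7.2; 41/0.80 − 41 = 10.3), which nothing in the documents supports. Those rows show the range, not an expectation. With q = 0 the error stays within 0.05 until f is about 4.7%, and with q = 0.10 until about 7.6%.

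The 16 of 41 example is the smallest rejecting count. At 17 of 41, six added failures are needed, and 18 of 41 still rejects after eight. This limits how often the choice of set matters, but not the direction of the bias.

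Last, keeping excluded subjects only when they fail pulls the rate slightly the other way: 24.9% for a true 25% with 5% early failures and 10% other exclusions. That is negligible.

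**Conclusion.** The concern holds. The deciding test uses a set from which some PFS failures are removed because they failed, and the study may replace them. For subjects who die or stop for clinical progression before Day 29, this follows from the text under either dose count, and the bias relative to all treated subjects is upward. For the Per-Protocol exclusions taken together, the bias is upward when the excluded fare worse than the 25% assumed for all treated.

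The size depends on two unknown shares and on reading 25% as an all-treated rate. With 5% to 10% excluded, type I error rises from 0.033 to between 0.043 and 0.079 over the values of q shown (0.10 and 0). At the cut-off, two or three dropped failures reverse the conclusion. The Kaplan-Meier figures assume no censoring before 6 months. This should be fixed; the planned ITT analysis reduces the harm but does not correct the decision rule.

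**What to change.** Amend SAP 3.2.2 and Protocol 4.1.2 and 3.1.11 as follows:
- Any treated subject who misses doses or an assessment because of death or progression, radiological or clinical, stays in the primary set as a failure and is not replaced.
- Documented death or clinical progression satisfies the disease-assessment condition.
- The 75% is stated to be counted either per drug or pooled.

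Report the ITT result of Table 14.2.1.2 beside the primary result, and say so if the two disagree on rejecting 25%.

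This needs wording changes only, with no new data or table, but the protocol part is an amendment that goes through the approvals in Protocol 7.2.5. The reported rate may be lower. Power at n = 41 stays at 82% if the 45% target is meant for all treated subjects. If 45% was meant only for the Per-Protocol set and all excluded subjects are failures, the rate with failures kept is 0.45(1 − f): 0.4275 at f = 5% gives 74% power, and 0.405 at f = 10% gives 63%.
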